9.2.1. Inclusion Criteria

Table 2. Summary of Inclusion Criteria

Inclusion Criteria	Assessment Period	Operational Definition	Rationale/Validated Source
Confirmed diagnosis of SCD	[Baseline]	1 inpatient medical claim with an International Classification of Diseases (ICD), Tenth Revision, Clinical Modification (ICD-10-CM) diagnosis code for SCD or 2 outpatient claims with an ICD-10-CM diagnosis code for SCD at least 30 days apart (including all genotypes as well as unknown type)	Administrative claims study ²⁰
Age between 12 and 85 years	[Index]	Age in years since year of birth	Age range covers the initial accelerated approval indication.
≥ 2 RBC transfusions	[Baseline]	At least 2 medical claims with an ICD Tenth Revision, Procedure Coding System (ICD-10-PCS) procedure code for an RBC transfusion at least 1 day apart (maximum 1 transfusion counted per day).	The subset of SCD patients who would most benefit from a reduction in RBC transfusion and necessary to measure a change from baseline to follow-up.
≥ 365 days of continuous enrollment during baseline and at least 180 days in follow up	[Baseline] [Follow Up	Both medical and pharmacy enrollment is required for observability (with a 45-day allowable gap between claims).	Observability is required to assess whether outcomes occurred and were not assumed to be missing.
≥ 180 days of continuous voxelotor use post-index (with 45-day gaps allowed) – voxelotor arm only	[Follow up]	At least 180 days of continuous voxelotor use post-index (with 45-day gaps allowed) defined using the voxelotor ship date and days supply reported on the claim— voxelotor arm only	Adequate exposure to voxelotor is necessary to evaluate the impact on RBC transfusions and other outcomes.

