Pfizer voluntarily withdrew voxelotor from the market on September 25, 2024, due to emerging preliminary data from clinical and registry-based real-world evidence (RWE) studies that showed the benefit of voxelotor no longer outweighs the risk; a comprehensive analysis of these studies is currently ongoing. In December 2022, voxelotor was recommended by the ASH Guideline Monitoring Expert Working Group for consideration as a preventive maintenance therapy to improve the baseline Hb of those with SCD at high risk of DHTR if RBC transfusion is required. The goal of this non-interventional, retrospective cohort study is to evaluate the effect of voxelotor on the reduction of RBC transfusions in individuals with SCD \geq 12 years of age in the US, who have a history of RBC transfusions using real-world data (RWD). The results from this study are intended to add to the totality of evidence for voxelotor pertaining to internal and external decision making for marketing authorization.

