9.2. Setting

The study population will include US patients with SCD between the ages of 12 and 85 years who are enrolled in a health insurance plan (commercial, Medicare, Medicaid) continuously during the 365 days prior to and including the index date (baseline) and 180 days post-index. The index selection period is November 25, 2019 (date of Food and Drug Administration [FDA] accelerated approval for voxelotor) through January 31, 2023. The exposed group will include patients with a new prescription claim for voxelotor (no prior use 365 days prior to index date), while the control group will include matched patients who do not have a prescription claim for voxelotor. Non-voxelotor controls will include those receiving no SCD-modifying therapies as well as those receiving non-voxelotor SCD treatments to be reflective of clinical practice. Patients who have a history of stroke will be excluded from this analysis. Both the exposed and control groups may be treated with other SOC treatments such as HU and have 2 or more documented RBC transfusions prior to study index.

Depending on the source of information, approximately 50% of individuals with SCD in the US have received a RBC transfusion, and approximately 20% have received a transfusion in the past year. ¹⁶ In the feasibility assessment of Komodo Healthcare Map (KHM) dataset, race/ethnicity was documented for 90% (n=2230/2486) of patients with 87% (n=1929/2230) identifying as Black or African American. The Centers for Disease Control and Prevention (CDC) estimates 90% of individuals with SCD in the US are non-Hispanic Black or African American. ¹⁷ Socioeconomic status also plays an important factor in impacting patient behavior and access to care. While the KHM dataset does not have direct measures of patients' socioeconomic status, important indicators will be leveraged in the analysis for patients including geography by region, health insurance type, and whether a hematologist is involved in the patient's care. KHM is nationally representative of individuals with SCD. In the Komodo data, approximately 68% of patients have Medicaid as their primary insurance type.

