After applying the inclusion/ exclusion criteria, to determine patient index date, the exposed group will index on the first voxelotor prescription claim date and will be sequentially matched using CEM with up to four non-voxelotor patients based on exact age (year) and calendar date to achieve balance between groups. ¹⁸ All exposed patients will be sampled before selecting control patients so that there will be no potential for voxelotor patients to be included in the control group. Age is a critical matching criterion, as individuals with SCD have better access to care before adulthood and accumulate comorbidities through the natural course of the disease. ¹⁹ The matched controls will be selected from the pool of patients who meet all the eligibility criteria below and are the same age (year) on the same day as the

voxelotor claim. Depending on available matches on the same date as the voxelotor claim, an age caliper may be considered to preserve sample size.

Voxelotor individuals will be matched in chronological order where up to four referent non-voxelotor controls will be identified for each voxelotor individuals before additional referent non-voxelotor matches are identified for the remaining exposure group individuals. Individuals will be sampled once to either the matched voxelotor or non-voxelotor cohort and contribute to one group only. This matching approach ensures that all referent individuals are matched to a voxelotor patient on the same date, mitigating potential selection bias by controlling for calendar time and thus any secular trends in available therapies, clinical guidelines, and other confounders that may occur during the study period (e.g., COVID-19 pandemic). Available matches depend on the number of eligible individuals available in the data source.

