Index Date1 Exposed: Prescription claim for voxelotor Inclusion Criteria (in prior 365 days): Control: Index date of voxelotor patient match ≥ 2 RBC transfusions Diagnosis of SCD **Exclusion Criteria:** Continuous Enrollment Stroke Pregnant at index Evidence of hemodialysis Continuous Voxelotor Evidence of hematopoietic stem cell transplantation or gene IO. 1801 therapy Inclusion Criteria Renal and/or liver transplant Inclusion/Exclusion Criteria 10.01 1-365, 01 Age ≥ 12 and ≤ 85 years Matching Criteria: Age **Patient Selection Matching Criteria** [0, 0] Covariate Assessment Period³ I-365, 01 **Outcome Assessment Period** [1. censor⁴] Start of study End of study period of interest November 2018 period of interest January 2024

Figure 1. Study Design Schematic

Abbreviations: RBC: Red blood cell; SCD: Sickle cell disease

 Index date for the exposed group will be the date of voxelotor prescription claim date and will be sequentially coarsened-exactmatched with up to 4 non-voxelotor patients based on age and calendar date.

Time

- Continuous voxelotor use defined using the voxelotor ship date and days supply with an allowable gap of at most 45 days (voxelotor arm only)
- 3. The full list of potential covariates including definitions can be found in Table 3.
- 4. Follow-up will end at the earliest of the following events: 365 days after index, death, disenrollment, the occurrence of any exclusion criteria events (e.g., pregnancy, stroke, hemodialysis, evidence of HSCT or gene therapy, renal transplant, or liver transplant), end of data, or discontinuation of voxelotor (voxelotor arm).

This study will use administrative closed claims data between November 2018 (one year prior to voxelotor FDA accelerated approval in the US) and the end of the study period (January 31, 2024; the matched controls will index on the same date of their matched

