9.7.3. Outcome Analysis

Operational definitions for each outcome are described below. Each outcome will be assessed using the primary assessment method for the follow-up period where follow-up will end on the earliest of the following occurrences:

- Disenrollment from health insurance (with a 45-day allowable gap)
- Death
- Discontinuation of voxelotor (with a 45-day allowable treatment gap, voxelotor arm only)
- End of follow-up: up to 1 year from index date (365 days)
- The occurrence of any exclusion criteria events (e.g., pregnancy, stroke, hemodialysis, evidence of HSCT or gene therapy, renal transplant, or liver transplant)

The primary analyses will employ an as-treated follow-up approach that ends follow-up upon treatment changes. Patients will be followed from the index date until treatment change (discontinuation of voxelotor for voxelotor group), or the end of follow-up, whichever is earlier. This as-treated method of analysis allows for an estimate of the effect while the patient is taking the drug of interest and addresses intercurrent events. However, it may introduce bias into the estimates. To adjust for differences in follow-up time between voxelotor patients and their matched controls, matched or pairwise censoring will be applied to censor unexposed on the date of voxelotor discontinuation for their matched pair as a sensitivity analysis.³⁸ A summary of sensitivity analyses is included in Table 7 to evaluate how the magnitude of this bias will be assessed.

Primary Objective - Change in Number of RBC Transfusions PPPY

For each patient, the difference in the number of RBC transfusions PPPY from baseline to follow-up period will be reported as the change and will be calculated as follows:

$$Change = \left(\frac{Number\ of\ RBC\ transfusions\ in\ follow-up}{Available\ days\ of\ follow-up} - \frac{Number\ of\ RBC\ transfusions\ in\ baseline}{365\ days\ *}\right)x\ 365$$

The change in the number of RBC transfusions PPPY will be analyzed using generalized linear model (GLM) with an identity link to estimate the difference in RBC transfusion change rates between the two groups. If any pre-index covariates that are found to be unbalanced after the PS method, it will be included in the regression as a covariate. The rate change and its 95% confidence intervals (CI) will be reported.

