For sensitivity analysis, transformations of the outcome may also be considered as appropriate. The outcome data will only be viewed overall prior to selecting a method of regression. 95% CI will be reported for the difference between the groups. Full details will be provided in the SAP.

Exploratory Objective 1 – SCD-related Complications Exploratory Objective 1.1 – Change in SCD-related Complications PPPY

VOCs, ACS, ACS + pneumonia, and priapism will be assessed as the change in the rate of events PPPY from baseline to follow-up. For each individual, the rate of each clinical outcome will be calculated as the number of events divided by the number of person-days. The change will be calculated as:

$$Change = \left(\frac{Number\ of\ events\ in\ follow-up}{Available\ days\ of\ follow-up} - \frac{Number\ of\ events\ in\ baseline}{365\ days\ *}\right)x\ 365$$
*All patients have 365 days of baseline data

The change in number of events PPPY will be analyzed using GLM with an identity link to estimate the difference in clinical outcome change rates between the two groups. If any preindex covariates that are found to be unbalanced after the PS method, it will be included in the regression as a covariate. The rate change and its 95% CI will be reported.

Exploratory Objective 1.2 – Time to Stroke

Stroke will be assessed as a time-to-event outcome. Cox proportional hazards (PH) models will be used to calculate the hazard ratio (HR); 95% CIs will be calculated using a robust variance estimator.

Exploratory Objective 2, Endpoint 1 – Number of RBC Transfusions PPPY in Follow-Up

The number of RBC transfusions that occur during the follow-up period will be assessed PPPY during available follow-up within each group. The mean number of RBC transfusions PPPY will be reported for each group. The mean difference between the groups will be assessed using a GLM similar to the primary analysis. The 95% CI will be reported for the difference between the groups.

Exploratory Objective 2, Endpoint 2 – Proportion of Patients with > 30% Reduction in RBC Transfusions

^{*}All patients have 365 days of baseline data

This outcome will be defined as the proportion of patients with a percent reduction in RBC transfusions between baseline and follow-up that is greater than 30%. For each patient, the percent change will be calculated as follows:

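### The 180-day post-index enrolment rule makes no exception for death, so early deaths and early fatal strokes drop out of both arms

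*Protocol*

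**What the plan says.** Protocol 9.2.1, Table 2, requires "365 days of continuous enrollment during baseline and at least 180 days in follow up". Section 9.2 says the same of the whole study population, which must be enrolled "continuously during the 365 days prior to and including the index date (baseline) and 180 days post-index", and the abstract repeats it. The row is not limited to one arm. The next row of Table 2, on continuous voxelotor use, is marked as applying to the voxelotor arm only. Controls are bound too: "The matched controls will be selected from the pool of patients who meet all the eligibility criteria below".

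The only tolerance in the enrolment row is "with a 45-day allowable gap between claims". Nothing is said about patients who die. The reason given there is observability of outcomes. The amendment log (section 5) adds that many voxelotor patients had little treatment, which could unbalance follow-up between the groups.

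Figure 1 opens the outcome window on day 1, and its footnote says: "Follow-up will end at the earliest of the following events: 365 days after index, death, disenrollment". Section 9.7.3 also lists death among the events that end follow-up, and Table 4 reports death as a frequency in follow-up. For exploratory objective 1.2, "Stroke will be assessed as a time-to-event outcome".

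**The concern.** A patient who dies on day 60 cannot be enrolled through day 180 and so never enters the cohort. Eligibility then depends on an event after index that treatment might affect. The follow-up death counts, and the stroke hazard ratio, describe only people who lived through roughly the first half of the year. A stroke followed by death in that period disappears together with the patient.

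Observability is a reason to remove people who leave their health plan, because their later outcomes are unseen. It is not a reason to remove people who die, whose course is complete at death. The amendment reason, short treatment and unequal follow-up, does not address death either.

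The omission is more than cosmetic because section 7 cites "studies that showed the benefit of voxelotor no longer outweighs the risk" as the ground for market withdrawal and says the results are meant to inform marketing-authorisation decisions. Section 9.1 also makes it a key consideration that the clinical benefit of transfusion should not worsen, and section 7 names stroke prevention among the uses of transfusion.

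**Working it through.** **1. Does the rule exclude early deaths?** The inputs are the 180-day requirement in both arms, a 45-day gap allowance, and an outcome window from day 1 to at most day 365.

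- Strict reading: death before day 180 means fewer than 180 days of enrolment, so the patient is not eligible.
- Loosest reading: if the 45-day gap could cover the end of the period without enrolment resuming, deaths from day 180 − 45 = 135 onward might still qualify. A gap normally implies that enrolment resumes, so this reading is generous.

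Deaths before about day 135 are lost on any reading.

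**2. What share of the year is affected?** 180/365 = 49.3%. On the loosest reading it is 135/365 = 37.0%.

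**3. How many deaths is that?** The protocol has no mortality figure to reproduce, so the following rests on assumptions. Let m be one-year mortality, assumed to lie between 0.5% and 5%, with a constant hazard h = −ln(1 − m)/365. The share of one-year deaths before day d is (1 − exp(−h·d))/m. The planned size of 185 + 370 = 555 (section 9.5) serves only as a scale.

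| Assumed m | Share removed, d = 180 | Deaths per 555 | Share removed, d = 135 | Deaths per 555 |
|---|---|---|---|---|
| 0.5% | 49.4% | 1.4 | 37.0% | 1.0 |
| 1% | 49.4% | 2.7 | 37.1% | 2.1 |
| 2% | 49.6% | 5.5 | 37.2% | 4.1 |
| 5% | 50.0% | 13.9 | 37.6% | 10.4 |

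**4. What of stroke?** Assume strokes are spread evenly over the year and that a fraction f of those in days 1 to 180 are fatal before day 180. The share of one-year strokes lost is about 0.493 × f. For f = 10% this is about 5%; for f = 50%, about 25%.

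**5. Could the hazard ratio move?** On the same assumptions, the observed ratio is about the true ratio × (1 − 0.493·f_treated)/(1 − 0.493·f_control). With a true ratio of 1.5:

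- f of 30% in treated and 10% in controls: 1.5 × 0.852/0.951 ≈ 1.34.
- The reverse: about 1.67.
- Equal f of 20% in both arms: 1.5, with events lost but no shift.

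The movement can go either way and needs early fatality to differ between arms.

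**6. Do the planned sensitivity analyses in Table 7 restore these patients?**

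- ITT reduces the voxelotor requirement to one claim. It does not say that the enrolment requirement is lifted.
- The subgroup with one year of minimum follow-up conditions on survival more strongly.
- Matched censoring acts on patients already selected.
- Sensitivity analyses apply to the primary endpoint unless stated otherwise, and neither ITT nor matched censoring is extended to stroke.

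None clearly brings the early deaths back. Section 9.9 and Annex Table 3 discuss differential censoring but not this survival condition.

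**The case against.** Much of the case on the other side stands and limits the point.

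- **Death is not an endpoint.** Table 5 does not list it, and Table 4 gives it as a descriptive frequency. Stroke is exploratory. The enrolment rule does not remove non-fatal early strokes.
- **The listing of death is not a contradiction.** A reader might infer that the protocol contradicts itself by naming death as a censoring event. It does not: death can still end follow-up after the restricted period, and the 180-day condition is openly stated in three places. What the documents lack is any acknowledgement that the condition removes early deaths.
- **No direction is shown.** A reader might infer that the rule flatters voxelotor. The protocol gives no mortality or stroke rate by arm, and both arms face the same enrolment rule. Bias needs early deaths that differ between arms, and the documents do not show that.
- **The share is conditional.** A reader might take 49% as a fact, or take it as certain that every death before day 180 is lost. The first rests on a constant hazard and the second on the strict reading of the gap.
- **The obvious repair is unsafe.** Adding a death exception to both Table 2 rows looks natural. But take a voxelotor patient who stops on day 40 and dies on day 100. The 45-day gap runs out on day 85, so this patient still fails the continuous-use row, while a control who dies on day 100 is kept. Early discontinuation is not rare: the amendment log reports that about 25% to 30% of voxelotor patients had no more than 30 days of treatment. Very short follow-up would also unsettle the primary analysis, for which 9.7.3 states no weighting: one transfusion in a patient who dies on day 10 annualises to 365/10 = 36.5 a year, against a planning standard deviation of 3.0.
- **Death capture is unknown.** Annex Table 1 gives no definition or source for death, so completeness cannot be judged from the protocol.

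These arguments change the remedy and lower the stakes. They do not supply a reason to leave early deaths uncounted.

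**Conclusion.** The point holds in a limited form. As written, the enrolment criterion conditions both arms on surviving about 180 days, or at least about 135 days on the loosest reading. Deaths and fatal strokes before then cannot appear in the follow-up death counts or in time to stroke, although outcomes run from day 1. That exclusion follows from the text alone.

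Its size does not. The range of about 37% to 50% of first-year deaths depends on an assumed constant hazard and assumed mortality of 0.5% to 5%. The direction of any bias is unknown, and the effect on the primary transfusion comparison may be small. The documents do not support a claim that the primary result is invalid or that the rule favours one arm. They do support a correction to how early deaths and strokes are reported, to the scope of the ITT analysis, and to the label on the main results.

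**What to change.** Keep the main cohort if the sponsor wishes, and do not simply add a death exception to the two Table 2 rows. Instead:

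1. Report deaths and strokes by arm from day 1 in the cohort that meets the baseline criteria only, before any post-index enrolment or persistence requirement. In the attrition table, show by arm how many patients each post-index requirement removes because of death.
2. State in Table 7 that the ITT sensitivity analysis drops both 180-day post-index requirements, follows patients from index to death or disenrolment, weights annualised rates by observed days, and also covers time to stroke.
3. Label the main results, including the Table 4 death counts and the stroke hazard ratio, as conditional on 180-day survival and enrolment, and add this to the limitations in 9.9.

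The cost is modest. Because 9.2 applies eligibility before matching, the cohort for items 1 and 2 needs its own run of matching and balance checks. Some patients with short follow-up will enter the sensitivity analysis, which is why the weighting is needed. The primary analysis is unchanged.

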Study size: The study will include all the eligible patients with an index date (defined as the date of a new voxelotor prescription claim for treated individuals, and the matched date for untreated individuals) from November 25, 2019, until January 31, 2023. An initial sample size assessment conducted with Komodo data through September 2023 identified ~94,000 patients with SCD, and among those patients, ~7,700 were treated with voxelotor. A conservative sample size estimate was calculated using a linear regression model with an adjustment factor of 1.65 which takes into account variance inflation in the analysis when propensity score adjustment will be applied. With 185 patients treated with voxelotor and 370 matched patients not treated with voxelotor (1:2 matching ratio), the study will have an 80% power to detect at least a 1-unit (1 RBC transfusion) difference between the two groups (standard deviation = 3.0) in the change in RBC transfusions PPPY from baseline to follow-up.

Data analysis: Baseline covariates will be evaluated in the 365 days prior to index date using descriptive statistics (continuous variables: mean, standard deviation, median, interquartile range; categorical variables: number of patients, percent). A PS model will be fit using logistic regression after baseline balance of covariates is assessed using absolute standardized differences and clinical input. A stepwise approach will be utilized to select the appropriate PS method based on diagnostic criteria to estimate the average treatment effect of the treated (ATT). For the primary analysis, an as-treated approach will be utilized and censoring criteria will include the following: disenrollment from health insurance (greater than 45-day gaps), death, discontinuation of voxelotor (with a 45-day allowable gap), or the occurrence of exclusion criteria.

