9.4. Data Sources

A data feasibility assessment was conducted using the Structured Process to Identify Fit-for-Purpose Data (SPIFD) framework to determine fit-for-purpose RWD sources for this study. 27 The study will use Komodo's Healthcare Map (KHM) database linked to Claritas prescription data (proprietary voxelotor claims) and Quest Diagnostics lab data. While Komodo data is de-identified, Komodo requires that all patients have tokens from the original personally identifiable information; Datavant is used for the tokenization process. These tokens are used to link the information from unique patients together from the KHM database, Claritas prescription data, and Quest Diagnostics lab data. Data sources are anchored on a closed system of administrative claims, including patient enrollment, physician, facility, and pharmacy claims. Administrative claims submitted for payment by providers and pharmacies are verified, adjudicated, and de-identified before inclusion. An initial data completeness check demonstrated full coverage for encounters based on ICD-10-CM codes and NDC on all continuously enrolled patients. Overall, claims data are expected to be a nearly complete capture of the patient's healthcare interactions, as claims restrict data inclusion to the time when patients are enrolled in both medical and pharmacy coverage. We expect minimal missing data on the treatment of interest (voxelotor) by linking the data from Komodo with Claritas Rx and high completeness of key data elements. However, guidance from Komodo recommends study periods end 9 months prior to the end of data to ensure complete capture of closed claims. Each data source is described in further detail below.

Pfizer has conducted a validation study²⁸ of RBC transfusions using the Optum Electronic Health Records and Claims Data among patients with SCD to support the use of procedure codes to identify these events in claims data, with the following objectives:

- To assess the concordance of RBC transfusion documentation based on medical claims data (ICD-10 procedure codes) compared to structured EHR data (and vice versa).
- To confirm RBC transfusions identified in structured EHR/claims data via procedures codes through clinical notes review.
- To identify and record the details of RBC transfusion administrations (specifically the reason for, type of transfusion and volume) and secondary complications of transfusions.

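### The 45-day enrolment gap is defined between claims in Table 2 but as a gap in insurance elsewhere, and either reading leaves a defect in eligibility or in the baseline rate

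*Protocol*

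**What the plan says.** The inclusion criterion in Table 2 (Section 9.2.1) is labelled as at least "365 days of continuous enrollment during baseline and at least 180 days in follow up". Its operational definition reads "Both medical and pharmacy enrollment is required for observability (with a 45-day allowable gap between claims", and its stated rationale is that observability is needed to tell whether outcomes occurred.

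Other sections describe the same requirement in terms of insurance:

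- Section 9.2 requires patients to be "enrolled in a health insurance plan (commercial, Medicare, Medicaid) continuously during the 365 days prior to and including the index date (baseline) and 180 days" after index.
- The censoring list in Section 9.7.3 has "Disenrollment from health insurance (with a 45-day allowable gap".
- The abstract has "disenrollment from health insurance (greater than 45-day gaps".
- Section 9.4 states "Data sources are anchored on a closed system of administrative claims, including patient enrollment, physician, facility, and pharmacy claims".

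The primary endpoint in Section 9.7.3 is the follow-up transfusion rate minus the baseline transfusion rate, scaled to a year. The baseline count is divided by a fixed 365 days, with the footnote "All patients have 365 days of baseline data". The follow-up count is divided by the available days of follow-up, a term that is not defined further. Section 9.7.1 treats the absence of a code as absence of the event.

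**The concern.** A gap between claims and a gap between coverage periods are different things, and they select different people. A fully insured control with no visit or fill for 46 days fails Table 2 as written but is still enrolled under Section 9.7.3. The Table 2 cell is the operational definition, so it is the text a programmer would code, and Section 9.8.1 says the protocol will be strictly followed.

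If the claims wording is coded, cohort entry depends on how often a patient uses care during the first 180 days of the outcome window. Transfusions are themselves identified from claims, so the outcome can help a patient qualify.

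If the coverage wording is coded, a patient can be uninsured for up to 45 days and still be admitted. Transfusions in that time would not be seen, yet the baseline formula counts those days as observed. The primary endpoint is a difference of two such rates.

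**Working it through.** The plan gives no figure of its own for this point, so there is none to reproduce. The inputs from the protocol are the 45-day gap (Table 2, Section 9.7.3, abstract), the 365-day baseline and 180-day minimum follow-up (Table 2), the fixed 365-day baseline denominator (Section 9.7.3) and the design difference of 1 transfusion per patient per year (Section 9.5).

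**Reading A: gap between claims.** Passing requires no interval longer than 45 days without a claim, through 180 days after index. How strongly this selects depends on claim frequency, which the protocol does not give. As an illustration only, suppose claims arrive at random (Poisson). The simulated share of fully insured patients passing the 180-day part is:

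| Assumed claims per year | Share passing 180 days |
|---|---|
| 12 | 12% |
| 24 | 55% |
| 36 | 84% |
| 52 | 97% |

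The range is too wide to establish an effect in this cohort. It shows only that the rule could select strongly or hardly at all. The selection happens after index, so a propensity score model on baseline covariates does not address it.

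**Reading B: gap between coverage periods.** Events on uncovered days are not recorded, so a rate that keeps those days in its denominator is understated by the fraction (gap days / denominator days).

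- Baseline, one full gap: 45/365 = 12.3%.
- Follow-up of 180 days, one full gap, if gap days are counted: 45/180 = 25.0%.
- Follow-up of 365 days, same condition: 45/365 = 12.3%.

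For one patient with an assumed constant true rate of 4 transfusions per year, the true change is 0. The calculated change becomes:

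- gap in baseline only: 4 × 45/365 = +0.49;
- gap in a 180-day follow-up only, if counted: −4 × 45/180 = −1.00;
- one gap in each: −1.00 + 0.49 = −0.51.

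These are shifts for one patient, not for a group mean. The between-arm effect is roughly (difference in gap prevalence) × (rate) × (fraction hidden). The prevalence is not given. With an assumed difference of 10 percentage points and rates of 4 to 12 per year:

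- smallest case: 0.10 × 4 × 45/365 = 0.05 per year;
- largest case: 0.10 × 12 × 45/180 = 0.30 per year.

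Against the design difference of 1, that is 5% to 30%. With equal prevalence and similar rates and follow-up in the arms, it largely cancels.

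**The two readings together.** Under reading A, a gap in an insured patient is observed time and belongs in the denominator. Under reading B, there is no selection on care use. Both defects would arise together only if coverage were inferred from claims, which the protocol does not say.

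**The case against.** The strongest reply is that the words in Table 2 are merely loose. The criterion is labelled as enrolment, its operational sentence begins with medical and pharmacy enrolment, Section 9.2 and the abstract describe plan enrolment, and Section 9.4 lists enrolment among the data and says claims data are restricted to time with both coverages. That makes the coverage reading the more plausible one. It does not remove the contradiction in an eligibility rule, and it leads straight to the denominator problem.

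A reader might go further and infer that the rule keeps only controls who use care heavily, raises their follow-up transfusion rate and so favours voxelotor. The documents do not support this. The literal rule would cover the 365-day baseline in both arms as well, and the endpoint is a change from baseline. The protocol gives no fill interval for voxelotor and does not say whether those fills, taken from the linked Claritas data, count toward the enrolment gap. Neither direction nor size can be derived.

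A reader might also take it as settled that gap days are counted in follow-up. They may not be: the available days of follow-up are undefined, and Section 9.7.3 leaves full detail to the SAP. The baseline denominator is different, because the protocol itself fixes it at 365.

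Finally, bridging short gaps is a legitimate choice. What does not follow from it is that the bridged days were observed.

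**Conclusion.** The point holds as a contradiction with a definite consequence under each reading. Table 2 conflicts with Section 9.7.3, the abstract and Section 9.2 on what the 45 days measure. If Table 2 is coded as written, entry is conditioned on post-index care use, with a bias of unknown size and direction. If the coverage meaning is intended, the baseline footnote is untrue for any patient with a permitted gap in that year, and one full gap understates that patient's baseline rate by 12.3%. The follow-up figure of up to 25% is conditional on gap days being counted and on the minimum 180-day follow-up.

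The effect on the treatment comparison is not established. The 0.05 to 0.30 per year shown above rests on an assumed 10-point difference in gap prevalence and assumed rates of 4 to 12 per year. This should be corrected before analysis, but it does not by itself show that the primary estimate is biased.

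**What to change.** In Table 2, define the 45-day allowance as a gap between medical and pharmacy enrolment spans, and use the same definition for disenrolment in Section 9.7.3. Use days with active enrolment as the denominator of both the baseline and the follow-up rate, and delete the footnote that all patients have 365 days of baseline data. The same footnote and fixed denominator appear in the formulas for exploratory objective 1.1 and for the percent reduction in transfusions, so those should change too.

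These changes belong in the protocol: eligibility and the primary formula are set there, and Section 9.7 says major modifications of primary endpoint definitions or analyses would be reflected in an amendment. The cost is an edit to the text, a small programming change using enrolment data that the source already holds, and baseline denominators that vary slightly between patients. Changing the denominators excludes no one.
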